STUDY PROTOCOL

Title: Evaluation of the Effects of Dexamethasone-Enriched Platelet-Rich Fibrin on Postoperative Pain, Edema, and Trismus Following Impacted Mandibular Third Molar Surgery: A Randomized Split-Mouth Clinical Trial

Principal Investigator: [name] [name]

NCT Number: Not yet assigned.

Affiliation: Department of Oral and Maxillofacial Surgery, Sivas Cumhuriyet University, Faculty of Dentistry, Sivas, Turkey

Document Date: June 18, 2023

1. Background and Rationale

Impacted mandibular third molar surgery often results in postoperative pain, swelling, and trismus, negatively affecting patient recovery. Platelet-rich fibrin (PRF) has been used to improve healing and reduce complications. This study investigates the enhanced effects of PRF prepared from blood enriched with dexamethasone, a corticosteroid with anti-inflammatory properties.

2. Objectives

- **Primary Objective:** To assess the effect of dexamethasone-enriched PRF on postoperative pain after mandibular third molar extraction.
- **Secondary Objectives:** To evaluate effects on postoperative edema, trismus, and analgesic consumption.

3. Study Design

A randomized, controlled, double-blind, split-mouth clinical trial. Each patient will receive both interventions in contralateral extraction sites: standard PRF vs dexamethasone-enriched PRF.

4. Participants

Inclusion Criteria:

- Healthy adults aged 18–25 years
- Bilateral symmetrical impacted mandibular third molars requiring extraction
- No systemic disease
- Good oral hygiene
- Provided written informed consent

Exclusion Criteria:

- Systemic or immunological disorders
- Recent corticosteroid or anti-inflammatory use
- Pregnancy or lactation
- Allergies to study medication
- Poor oral hygiene or active oral infections
- Temporomandibular joint disorders affecting mouth opening

5. Interventions

- Control: PRF prepared from standard venous blood.
- Test: PRF prepared from venous blood mixed with 4 mg dexamethasone sodium phosphate prior to centrifugation.

6. Outcome Measures

- **Primary Outcome:** Postoperative pain measured by Visual Analog Scale (VAS) at 24, 48, and 72 hours.
- **Secondary Outcomes:** Edema, trismus, and analgesic consumption measured on postoperative days 1, 3, and 7.

7. Sample Size

Sixteen patients (32 extraction sites) based on power calculation.

8. Statistical Analysis

SPSS 22.0; Independent samples t-test or Mann–Whitney U test depending on data distribution. Significance threshold $p < 0.05$.

9. Ethics

Approved by Sivas Cumhuriyet University Ethics Committee (Approval No: 2023-07/02, Date: 18.07.2023). Written informed consent obtained.

10. Data Confidentiality

Anonymized data storage, access limited to study personnel, data retained for 5 years.

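### The plan sets no balance over side or operation order for its 16 patients and does not adjust for either, so a chance imbalance can distort the drug comparison in the sample obtained

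*Combined protocol and SAP*

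**What the plan says.** Section 3 (Study Design) calls the study "A randomized, controlled, double-blind, split-mouth clinical trial" and adds: "Each patient will receive both interventions in contralateral extraction sites: standard PRF vs dexamethasone-enriched PRF". Section 7 (Sample Size) gives "Sixteen patients (32 extraction sites) based on power calculation". Section 8 (Statistical Analysis) names "Independent samples t-test or Mann–Whitney U test depending on data distribution". The primary outcome in Section 6 is "Postoperative pain measured by Visual Analog Scale (VAS) at 24, 48, and 72 hours".

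The document does not say how the sequence is generated or concealed, or whether side, order or both are randomised. It sets no balance on either. It also does not say whether the two sides are operated on in one session or two.

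**The concern.** Within a patient, factors such as pain threshold act on both sites and cancel in the difference. Side of the mouth does not cancel, and nor does order if one side is done before the other. These cancel only across patients, and exactly only if the test product is equally often on each side and in each position.

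With 16 patients, chance alone cannot be relied on for that balance, and the planned analysis would not correct an uneven split. Part of any side or order effect would then sit inside the estimated drug effect on a subjective pain score. Once patients are enrolled, the design can no longer repair this.

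**Working it through.** **The plan's own figure.** The 16 patients cannot be reproduced, because no effect size, SD, power, correlation or sidedness is given. Back-solving at two-sided 0.05 and 80% power (both assumed, normal approximation): an unpaired comparison needs d = (1.960 + 0.842) × √(2/16) = 0.99; a paired one needs d_z = (1.960 + 0.842)/√16 = 0.70. Neither settles how patients were to be allocated.

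**Inputs.** n = 16 (Section 7); one test and one control site per patient (Section 3). Simple randomisation is an assumption. So is the size of the side or order effect: Δ = 0, 0.25, 0.5 and 1.0, in SDs of the within-patient difference.

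**Chance of imbalance on one factor**, Binomial(16, 0.5), 2^16 = 65,536:
- exactly 8:8: 12,870/65,536 = 19.6%
- 10:6 or worse: 1 − (12,870 + 2 × 11,440)/65,536 = 45.4%
- 12:4 or worse: 2 × 2,517/65,536 = 7.7%

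If side and order were randomised independently, at least one would be 12:4 or worse with probability 1 − (1 − 0.0768)² = 14.8%, and both exactly 8:8 with probability 0.196² = 3.9%.

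**Share entering the drug estimate.** With k patients having the test product on the higher-scoring side, the estimate shifts by Δ × (2k/16 − 1): 12.5% of Δ at 9:7, 25% at 10:6, 50% at 12:4. The sign is random and the average is zero.

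**Effect on precision and power** (100,000 simulated trials, one factor, paired t-test; power at an assumed drug effect of 0.8 SD; the term is for side). For simple randomisation the SD of the estimate is 0.25 × √(1 + Δ²), which the simulation matches to within 0.001; under 8:8 it is 0.25.

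| Δ | SD of estimate, simple | SD of estimate, 8:8 | Power, simple, no term | Power, 8:8, no term | Power, simple, with term | Power, 8:8, with term |
|---|---|---|---|---|---|---|
| 0 | 0.25 | 0.25 | 85.0% | 85.0% | 81.9% | 84.6% |
| 0.25 | 0.26 | 0.25 | 82.5% | 83.1% | 81.7% | 84.4% |
| 0.5 | 0.28 | 0.25 | 76.3% | 78.1% | 82.0% | 84.5% |
| 1.0 | 0.35 | 0.25 | 55.4% | 56.5% | 82.0% | 84.7% |

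**Type I error, paired t-test without a term.** Over all simple randomisations it is 4.9% to 5.0% at every Δ. Among trials that happen to split 12:4 or worse, it is 7.4%, 14.0% and 29.1% at Δ = 0.25, 0.5 and 1.0. Under 8:8 without a term it falls to 4.4%, 2.9% and 0.6%.

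**Type I error under the planned unpaired t-test.** With an assumed within-patient correlation of 0.5, the SD of the difference is √(2 × 0.5) = 1 site SD. At a right-left difference of that size, type I error is 3.1% with simple randomisation and 0.3% with 8:8. Balance without a matching analysis only makes the test more conservative.

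**The case against.** A reader might infer that the trial allocates by coin toss. The document does not say so. A balanced list may be intended and simply not described, and every probability above depends on that assumption. This stands; what can be said is that the plan permits an unbalanced allocation.

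A reader might also infer that any side or order effect passes into the drug effect, or that the trial is biased. Neither is supported. Only |2k/16 − 1| of the effect enters, and all of it only at 16:0. In 54.5% of simple randomisations (8:8 or 9:7) the share is at most 12.5%. The sign is random, the estimator is unbiased, and the paired test holds its level on average. This stands too, but it does not help with the one allocation that has to be interpreted.

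The size of the problem is unknown. Section 4 requires matching impactions on the two sides, which limits anatomical differences, and order matters only if the sides are operated on in sequence. Analgesic consumption, a secondary outcome, is hard to attribute to one product unless the sides are treated on separate occasions, which suggests that order does apply, but the document does not say so.

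Finally, adjustment alone recovers much of the loss: at Δ = 0.5, a side term under simple randomisation raises power from 76.3% to 82.0%. Imbalance can therefore be handled partly in the analysis. Balance adds the rest (84.5%), and it makes the term almost free when there is no side effect (84.6%, against 81.9% under simple randomisation).

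**Conclusion.** The point holds as a cheap improvement. Section 3 does not constrain the allocation over side or order, and Section 8 does not adjust for them. Under simple randomisation (assumed), one factor would be 10:6 or worse in 45.4% of trials and 12:4 or worse in 7.7%. The consequence is extra variance and a conditional distortion in the sample obtained. For assumed shifts of 0 to 1.0 SD, balance takes the SD of the estimate from between 0.25 and 0.35 down to 0.25.

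It would be wrong to conclude that a single 8:8 split solves this at no cost. One such split balances one factor only, and it improves the test materially only if the analysis is paired and carries the matching term.

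**What to change.** **Section 3.** State that patients are allocated from a computer-generated list made before the first patient, with four patients in each of the four cells of test side (left or right) by test order (first or second): 4 × 4 = 16. If order does not apply, use 8:8 on side. Keep the list concealed, and let only the person preparing the PRF see each assignment, opened after consent and eligibility are confirmed. Record side and order for every operation. If a balanced list already exists, describe it.

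**Section 8.** Replace the unpaired test with an analysis of the within-patient difference (test minus control) that includes side and order terms. With four patients per cell the terms are uncorrelated with each other and with the drug effect.

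**Cost.** No extra patients. Each term takes about one degree of freedom; for one term, power goes from 85.0% to 84.6% if there is no side effect. With both terms, 16 − 3 = 13 degrees of freedom remain. The last allocations in a fixed list become more predictable if masking fails. Dropout can break exact balance, in which case the side and order terms still adjust for what remains.

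### The primary pain outcome is read at three times with no rule for what counts as positive; if any one time suffices, correctly paired tests give a 9–14% false-positive rate

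*Combined protocol and SAP*

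**What the plan says.** Section 2 (Objectives) has one primary objective, with no time attached: "To assess the effect of dexamethasone-enriched PRF on postoperative pain after mandibular third molar extraction". Section 6 (Outcome Measures) gives the matching primary outcome as "Postoperative pain measured by Visual Analog Scale (VAS) at 24, 48, and 72 hours".

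Section 8 (Statistical Analysis) names the software, the tests ("Independent samples t-test or Mann–Whitney U test depending on data distribution") and a 0.05 significance threshold, and nothing more. Section 3 (Study Design) states that "Each patient will receive both interventions in contralateral extraction sites", so the data are paired within patient. Section 7 (Sample Size) reads "Sixteen patients (32 extraction sites) based on power calculation", without the endpoint, effect size, standard deviation or power behind it.

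The remaining sections add nothing on this point. Nowhere is there a primary time, a summary over times, a testing order, a multiplicity adjustment or a definition of a positive primary result.

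**The concern.** The tests in Section 8 compare one set of values per treatment. The primary outcome supplies three sets, and the plan does not say which is tested or how three results become one conclusion. One, two or three significant times could each be reported as success on the primary outcome, and nothing prevents that choice from following the results.

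The trial's only primary claim is at stake. Its false-positive rate depends on a rule nobody has written down, and a reader of the results could not tell a planned pain finding from the best of three.

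**Working it through.** **Inputs from the documents.** Three primary times (Section 6); significance level 0.05 (Section 8; two-sided assumed, since sidedness is not stated); 16 patients, hence 16 pairs (Sections 3 and 7). The plan states no overall error rate, so there is no figure of its own to reproduce. The sample size cannot be reproduced either, because its inputs are not given.

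**Assumption.** The correlation ρ between a patient's test-minus-control differences at different times is not in the documents, so a range is shown.

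**Step 1: limits at ρ = 0.**
- Any one of three significant: 1 − 0.95³ = 1 − 0.857375 = 14.26%.
- Any one significant in favour of the test treatment: 1 − 0.975³ = 7.3%, against a nominal 2.5%.
- All three significant: 0.05³ = 0.0125%.

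**Step 2: paired t-tests with correlated times.** Simulation with no true effect, 16 pairs, three equally correlated normal differences, t on 15 df, 200,000 trials per setting:

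| Success rule | ρ = 0 | 0.3 | 0.5 | 0.7 | 0.9 |
|---|---|---|---|---|---|
| Any one of three, two-sided | 14.3% | 13.6% | 12.8% | 11.1% | 8.6% |
| Any one of three, benefit only | 7.4% | 6.9% | 6.4% | 5.7% | 4.3% |
| All three | 0.01% | 0.08% | 0.3% | 0.8% | 2.1% |

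A first-order autoregressive pattern gives similar any-one values (13.1% at 0.5, 8.9% at 0.9). Only near-perfect correlation brings the any-one rate close to 5% (6.1% at ρ = 0.99).

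**Step 3: the independent t-tests as written.** Let r be the correlation between a patient's two sides. The unpaired test takes the variance of the mean difference as 2σ²/16, when it is really 2σ²(1 − r)/16. The test statistic is therefore too small by a factor of √(1 − r), which is 0.71 at r = 0.5. Simulated error for any one of three, with between-time correlation from 0.7 down to 0.3 (60,000 trials per setting):

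| Side correlation r | Any one of three |
|---|---|
| 0 | 10.9–13.8% |
| 0.3 | 4.9–6.1% |
| 0.5 | 2.0–2.3% |

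At r = 0.7 a separate run gave 0.2–0.4%. Rounding to an integer 0–10 scale changes little (11.2–14.0%, 5.2–6.2% and 2.3–2.5% for r = 0, 0.3 and 0.5).

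**Step 4: power of the candidate rules.** The mean of three equally correlated differences, each with SD 1, has SD √((1 + 2ρ)/3), which is 0.816 at ρ = 0.5. With an effect of 0.6 SD at every time, the noncentrality is √16 × 0.6/0.816 = 2.94, giving 78% power on 15 df. With 0.6 SD at 24 h only, the mean effect is 0.2, the noncentrality is 0.98 and power is 15%. Bonferroni tests each time at 0.05/3 = 0.0167. Holm finds at least one significant time exactly when Bonferroni does, so the last column applies to both.

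| Effect at 24 / 48 / 72 h (SD of differences) | Mean of three times, ρ = 0.3 / 0.5 / 0.7 | Any of three, Bonferroni, ρ = 0.3 / 0.5 / 0.7 |
|---|---|---|
| 0.6 / 0.6 / 0.6 | 87 / 78 / 71% | 73 / 68 / 62% |
| 0.6 / 0 / 0 | 18 / 15 / 13% | 43% throughout |
| 0.8 / 0.4 / 0 | 54 / 45 / 39% | 73 / 71 / 70% |

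**The case against.** The strongest reply is that 9–14% belongs to a plan nobody wrote. It needs an any-one-of-three rule, which the protocol does not state, and paired tests, which it does not specify. Under the unpaired tests it does specify, the any-one rate is near or below 5% once the two sides correlate at about 0.3 or more. The range also rests on assumed correlations: its upper end needs uncorrelated differences a day apart in the same socket, and for claims of benefit alone the rate is 4.3–7.4%. Section 8 does not actually say that each time is tested separately; a two-group test could be applied to an average over 24–72 h. Finally, the documents give no basis for preferring the average, which performs poorly if benefit is confined to 24 h.

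Much of this stands as a limit on what can be claimed. The plan is silent rather than committed to three tests, the error rate as written is not demonstrably inflated, and the choice among valid rules belongs to the sponsor. None of it supplies the missing rule. Conservatism that comes from ignoring the pairing is accidental, depends on an unknown correlation, and vanishes once the analysis is matched to the split-mouth design. Nor can the three readings be treated as descriptive: Section 6 labels them the primary outcome.

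**Conclusion.** The concern holds and should be settled before analysis. The plan has one primary pain claim, three measurements and no decision rule, so the error rate of that claim is uncontrolled. With correctly paired tests, the unstated rule alone moves the two-sided false-positive rate from near 0 (all three required) to 14% (any one suffices, uncorrelated times). The any-one reading gives about 9–14% for between-time correlations from 0.9 down to 0.

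These figures assume normal differences, equal correlation between times, 16 complete pairs and two-sided testing. With the independent t-tests as written, the any-one rate runs from about 2% to 14% for side correlations of 0.5 down to 0. The absence of a rule is a defect under either test.

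**What to change.** Write one decision rule into Sections 6 and 8 before the data are analysed, and correct the pairing in the same edit.

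- **Suggested default:** for each patient, take the test-minus-control difference in mean VAS (or area under the curve) over 24, 48 and 72 h, and test it once with a paired t-test at two-sided 0.05. State a paired rank alternative, such as the Wilcoxon signed-rank test, in place of the Mann–Whitney provision. Report the three time-specific paired differences with 95% confidence intervals as secondary.
- **If the effect is expected mainly at one time:** name that time as primary, or test all three paired differences with Holm adjustment. Either controls the error.
- **If a mixed model is preferred:** include a patient-by-treatment random effect as well as the patient effect. In balanced null simulations (30,000 trials), a patient intercept alone gave type I error of 14.7, 21.6 and 28.6% at between-time correlations of 0.3, 0.5 and 0.7, against 4.8–5.1% for the paired test on averages.

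All three readings are already planned, so no data collection changes. The sample-size statement in Section 7 must be rechecked against the chosen rule. Each choice has a price in power: the average loses heavily if the effect is confined to one time (about 15% against 43% at correlation 0.5), while Holm or Bonferroni gives up about 9–14 percentage points if the effect is equal at all three.

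### Does leaving the session schedule unstated make the analgesic-consumption comparison untestable?

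*Combined protocol and SAP*

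**What the plan says.** Section 3 describes a split-mouth design: "Each patient will receive both interventions in contralateral extraction sites: standard PRF vs dexamethasone-enriched PRF". Section 7 gives the size: "Sixteen patients (32 extraction sites) based on power calculation". Section 2 sets the secondary objectives: "To evaluate effects on postoperative edema, trismus, and analgesic consumption". Section 6 gives their timing, listing edema and trismus together with "analgesic consumption measured on postoperative days 1, 3, and 7". The primary outcome, VAS pain, is read at 24, 48 and 72 hours. Section 8 names the tests: "Independent samples t-test or Mann–Whitney U test depending on data distribution".

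No section states whether the two extractions share a session, what interval or order of sides applies if they do not, how analgesic intake is assigned to a side, or what period each intake record covers. Trismus has no stated measure. The only hint is an exclusion in Section 4, "Temporomandibular joint disorders affecting mouth opening", which makes mouth opening plausible but does not settle it.

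**The concern.** Swelling and, with some care, pain can be recorded for one side of the mouth. Tablets cannot, because the patient takes them for whatever hurts. If both sides were operated on together, each intake record would be one number per patient with no link to either intervention, yet Section 8 offers only two-group tests. An analyst who entered the same number for both sides would obtain a null result whatever the true effect, and a stated objective would have gone untested. Trismus would be in the same position if it is measured as mouth opening.

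If the sides are operated on separately but close together, part of the first side's recorded intake would be due to the second operation. At short intervals the primary VAS readings would be affected too. With the recording period undefined, a reader also could not tell whether a day 7 figure means one day's tablets or a week's.

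**Working it through.** **Inputs.** From the protocol: 16 patients and 32 sites (Section 7); intake records on days 1, 3 and 7 and VAS at 24, 48 and 72 h (Section 6); independent-samples t-test or Mann–Whitney U at 0.05 (Section 8). Assumed: the session schedule, the recording period, and that day n ends at 24n hours. Section 7 gives no inputs to its power calculation, so 16 cannot be reproduced; this point does not depend on it.

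**1. One session.** Each record day yields 16 patient values, so 3 × 16 = 48 records in all, none belonging to an intervention. The between-side effect is not estimable. If each value is nevertheless entered in both groups, the mean difference is 0, t = 0, U = 16 × 16 / 2 = 128 and p = 1. (If all 16 values were equal, t would be 0/0; U and its p-value would not change.) Simulated counts give the same result every time, as they must: two identical columns cannot differ. This describes a data-entry choice and measures nothing about the plan.

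**2. Separate sessions.** Each record day yields 16 values per side, so 3 × 32 = 96 records, and the contrast can be estimated. As an illustration, take a true difference of 1 SD, 16 patients, two-sided 0.05 and within-patient correlation from 0 to 0.7 (all but the 16 and the 0.05 assumed). In simulation the independent t-test has power of about 78% to 90%, and a paired t-test about 76% to 99.7%. The test named in Section 8 can therefore detect a difference.

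**3. Overlap.** Let the second operation fall on day k after the first, and count a record due that day as taken beforehand. First-side records that fall after the second operation:

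| k (days) | Intake records (of 3) | VAS readings (of 3) |
|---|---|---|
| 0 | 3 | 3 |
| 1 | 2 | 2 |
| 2 | 2 | 1 |
| 3–6 | 1 | 0 |
| 7 or more | 0 | 0 |

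Overlap matters only at short intervals, and the protocol does not say that the interval is short.

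**4. Recording period.** Hours covered by the three records:

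| Reading | Day 1 | Day 3 | Day 7 |
|---|---|---|---|
| That day only | 24 | 24 | 24 |
| Since the last record | 24 | 48 | 96 |
| Cumulative | 24 | 72 | 168 |

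At constant intake the day 3 figure would vary as 24:48:72 = 1:2:3 and the day 7 figure as 24:96:168 = 1:4:7. Constant intake over a week is itself an assumption with no support in the document. More to the point, the ratios compare one definition with another. Within any one definition, the test and control sides are recorded over the same hours, so the between-side contrast is fair. The definition fixes which quantity is being compared and introduces no bias.

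**5. Which schedule fits the text.** Section 2 treats intake as something the interventions may affect differently, and Section 6 times it from an operation. Both fit one operation and one recovery per side. Under a single session the objective has no content. This is inference, since the protocol does not say so, but it is the reading under which the sections agree with each other.

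**The case for a change.** The strongest case for a change is that the schedule decides whether a named objective can be tested at all, that stating it would take a few sentences, and that intake not recorded by side and period may be impossible to reconstruct afterwards. All of that is true. Overlap at short intervals would also reach the primary outcome, so the matter is not confined to a minor endpoint.

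What stands is that the protocol is thin here, and that a reader of the results will need the session schedule, the order of sides and the recording period. What does not stand is that the plan leads to an invalid analysis. That would require the investigators to operate on both sides together and then to enter one total twice. The first is not stated; the second is a step that an analyst holding one number per patient would have no reason to take, since reporting it once per patient is the evident course.

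A remedy that required the first side's day 7 record before the second operation would in effect set a minimum interval between operations, which is for the investigators. Preferring a signed-rank test on within-patient differences raises a different question: whether independent-samples tests suit split-mouth data. That question touches every outcome and does not depend on the session schedule.

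**Conclusion.** No change to the plan follows. Sections 3 and 6 omit the session schedule, the order of sides, the attribution of intake and the period of each record. These are details the investigators must settle in order to run the trial, and writing them down would clarify the reporting without altering the design or the analysis.

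With separate sessions and recoveries that do not overlap, the comparison is valid, with 16 values per side at each record day. With a single session, intake (and trismus, if measured as mouth opening) could only be described per patient, and that part of the secondary objective would fall away; the document does not establish that this is the case. The p = 1 result is a property of duplicated data, and the 3-fold and 7-fold ranges are differences of definition. Neither measures harm to the trial, and the document gives no basis for estimating the treatment effect on intake.

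The conclusion rests on reading Sections 2 and 6 as implying one operation and recovery per side, and on the same recording period being used for both.

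### Section 8 plans only independent-groups tests for a split-mouth trial of 16 matched pairs, so its p-values are miscalibrated whenever a patient's two sides are correlated.

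*Combined protocol and SAP*

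**What the plan says.** - **Section 3 (Study Design):** the trial is split-mouth. "Each patient will receive both interventions in contralateral extraction sites: standard PRF vs dexamethasone-enriched PRF"
- **Section 6 (Outcome Measures):** the primary outcome is "Postoperative pain measured by Visual Analog Scale (VAS) at 24, 48, and 72 hours". The secondary outcomes are "Edema, trismus, and analgesic consumption measured on postoperative days 1, 3, and 7".
- **Section 7 (Sample Size):** "Sixteen patients (32 extraction sites) based on power calculation". No effect size, SD, power or correlation is given.
- **Section 8 (Statistical Analysis):** "Independent samples t-test or Mann–Whitney U test depending on data distribution", with a significance threshold of 0.05. No paired test, mixed model or other allowance for two observations per patient is named here or elsewhere. The section also does not say how the tests apply to the three pain time points.

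**The concern.** The design and the analysis contradict each other. Both tests in Section 8 assume that the two sets of observations come from unrelated people. In this trial each control observation has a partner from the same person, who has the same pain threshold, scoring habits and healing. The standard error of the treatment difference should reflect that link, and the planned tests ignore it. Choosing Mann–Whitney over the t-test does not help, because it ignores the pairing too.

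With 16 patients, pairing is the main efficiency gain of a split-mouth design. If it is discarded, a null result on pain is hard to read: there may be no effect, or the test may have thrown away the information needed to see one. It also leaves room for a switch to paired tests after the data are seen.

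**Working it through.** **Inputs from the documents:** 16 patients and 32 sites (Section 7), both treatments in every patient (Section 3), threshold 0.05 (Section 8).

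**Assumptions, not in the documents:** 16 complete pairs, normal data, equal SD on both sides, a two-sided test, within-patient correlation rho, and effect d in single-side SDs.

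**The plan's own figure.** The 16 patients cannot be reproduced, because Section 7 gives no inputs. Working backwards at 80% power and two-sided 0.05, 16 per group in an independent comparison detects d = 1.02, while 16 pairs detect a mean difference of 0.75 SDs of the differences. Nothing shows which comparison was intended.

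**Step 1: the standard error.** With n pairs:

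- true variance of the mean difference: 2·SD²·(1 − rho)/n
- variance the independent test assumes: 2·SD²/n
- ratio of assumed to true standard error: 1/√(1 − rho)

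The ratio is 1/√0.7 = 1.20 at rho 0.3, 1/√0.5 = 1.41 at 0.5 and 1/√0.3 = 1.83 at 0.7. It equals 1 only at rho = 0. The independent t-test uses 30 degrees of freedom and the paired t-test 15. The critical values are 2.042 and 2.131, so the paired test pays a small price that the smaller standard error soon outweighs.

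**Step 2: type I error and power.** Simulation of 200,000 trials per cell. Power is shown as paired v planned t-test.

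| rho | Type I error, planned t-test | Power, d = 0.6 | Power, d = 0.8 | Power, d = 1.02 |
|---|---|---|---|---|
| 0 | 5.0% | – | 56% v 59% | 77% v 80% |
| 0.1 | 3.9% | – | 61% v 60% | 81% v 81% |
| 0.2 | 3.0% | 43% v 36% | 66% v 60% | 85% v 82% |
| 0.3 | 2.2% | 47% v 36% | 71% v 61% | 90% v 84% |
| 0.5 | 0.8% | 61% v 34% | 85% v 63% | 97% v 87% |
| 0.7 | 0.1% | 82% v 31% | 97% v 65% | 99.8% v 92% |

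The paired t-test keeps its type I error at about 5% at every rho. Its simulated power agrees within 0.3 points with the exact non-central t, whose non-centrality is d·√n/√(2(1 − rho)). For d = 0.8 and rho = 0.5 that is 0.8 × 4/1 = 3.2 on 15 degrees of freedom, giving 85%. At d = 0.8 the two tests break even at about rho 0.07.

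**Step 3: the rank tests.** With 20,000 trials per cell and exact critical values, Mann–Whitney's type I error is 2.0%, 0.7% and 0.2% at rho 0.3, 0.5 and 0.7. Power at d = 0.8, Wilcoxon signed-rank v Mann–Whitney, is 67% v 57%, 82% v 58% and 96% v 61%.

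**Step 4: negative correlation.** At rho −0.3 the planned t-test's type I error is about 8.4%. This is unlikely for scores from one person, but it shows that the planned test is not conservative in every case.

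**The case against.** The strongest reply is that the error is on the safe side. Under the expected positive correlation the planned tests reject too rarely, so a significant result would remain credible. The loss also rests on a correlation and an effect that the documents do not give. At a large effect it is modest: at d = 1.02 and rho 0.3 it is 90% v 84%, and at d = 1.2 and rho 0.3 it is 96.6% v 94.1%. This stands as a limit on the size. No cell in the table is an estimate for this trial. It does not remove the mismatch: at moderate effects the loss is substantial from about rho 0.3, and a cheap, correctly calibrated test is available.

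A second reply is that paired tests at each of 24, 48 and 72 hours leave multiplicity open. Three calibrated tests at 0.05 would give at least one false positive in 1 − 0.95³ = 14% of trials if the times were independent, and fewer if they are correlated. That is true, and the conservatism of the planned tests partly hides it. It is a separate gap in the existing plan, which names neither a primary time point nor a rule for combining the three, and it is no reason to keep tests that ignore the pairing.

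A third reply is that, if the sides are operated on in separate sessions, a simple paired test ignores order. The documents do not say whether they are. The point is fair and can be settled in the same revision.

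**Conclusion.** The concern holds. The only tests planned for the primary outcome assume independent groups, while the design produces 16 matched pairs. This is wrong as written, not merely unspecified.

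Under positive correlation the consequence is lost power, not inflated false positives. At 0.8 SD the paired t-test gains about 10 points at rho 0.3 (71% − 61%), 22 at rho 0.5 (85% − 63%) and 32 at rho 0.7 (97% − 65%). The difference is negligible below about rho 0.1, and smaller at effects near 1 SD. These figures assume normal data, equal SDs, complete pairs and a two-sided 0.05 level. The mismatch itself depends on none of these assumptions. It must be corrected before analysis.

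**What to change.** **Section 8.** Replace the independent-groups tests with one of the following, and state in advance which is primary:

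- a paired t-test on within-patient differences at 24, 48 and 72 hours, with the distribution checked on the differences and Wilcoxon signed-rank as the non-parametric alternative; or
- a linear mixed model with treatment, time and their interaction, a random patient effect, and a side-within-patient effect, because each side gives three scores.

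Report the mean within-patient difference with its 95% confidence interval for each outcome recorded separately by side or by operation. For trismus and analgesic consumption, first state whether a per-side value exists, which depends on whether the two sides are operated on in separate sessions. The same revision is the place to name the primary pain time point or a multiplicity rule.

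**Section 7.** Describe the sample as 16 pairs. If the power calculation was made for independent groups, restate it for the paired test with the assumed SD of the differences.

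**Cost.** A few sentences in two sections, plus an assumed SD of the differences if the calculation has to be restated. No new patients or data. If the correlation is truly zero, the paired test gives up about 3 points of power (56% v 59% at 0.8 SD, 77% v 80% at 1.02 SD).
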